### 9.2 FILE MANAGEMENT AT THE STUDY SITE

It is the responsibility of the Investigator to ensure that the study center file is maintained in accordance with Section 8 – Essential Documents for the Conduct of a Clinical Trial of the ICH Guidance for Industry E6 Good Clinical Practice: Consolidated Guidance and 21 CFR Part 312.

### 9.3 RECORDS RETENTION AT THE STUDY SITE

It is a Novan requirement that all Investigators participating in clinical studies maintain detailed clinical data for one of the following periods, whichever is longest:

- Country-specific requirements; or
- A period of at least two years following the last approval of a marketing application approved by a Regulatory Authority in an ICH region or until there are no pending or contemplated marketing applications in an ICH region; or,
- A period of two years after Novan notifies the Investigator that the data will not be submitted for review by any Regulatory Authority.

The Investigator must not dispose of any records or essential documents relevant to this study without either (1) written permission from Novan, or (2) providing an opportunity for Novan to collect such records. The Investigator shall take responsibility for maintaining adequate and accurate electronic or hard copy source documents of all observations and data generated during this study. Such documentation is subject to inspection by Novan and relevant regulatory agencies. If the Investigator withdraws from the study (e.g., relocation, retirement), all study-related records should be transferred to a mutually agreed-upon designee. Notice of such transfer will be provided to Novan in writing.

# 10. MONITORING, COMPLIANCE, AND QUALITY

All aspects of the study will be monitored by PPD or Novan according to Good Clinical Practices (GCP) and Standard Operating Procedures (SOPs) for compliance with applicable government regulations, (i.e., informed consent regulations, (21 C.F.R. § 50.20, 1999), and Institutional Review Board regulations, (21 C.F.R. § 56.103, 1981)). Access to all records, both during the trial and after trial completion, should be made available to PPD and Novan at any time for review and audit to ensure the integrity of the data. The Investigator must notify PPD immediately if the responsible IRB has been disqualified or if proceedings leading to disqualification have begun.

The Investigator must conduct the protocol in accordance with applicable GCP regulations and guidelines, applicable informed consent regulations (21 C.F.R. § 50.20, 1999), and in compliance with the principles in the Declaration of Helsinki. Every attempt must be made to follow the protocol and to obtain and record all data requested for each subject at the specified times. If data is not recorded per protocol, the reason(s) must be clearly documented on the study records.

Before study initiation, at a site initiation visit or at a meeting with the Investigator(s), a PPD or Novan representative will review the protocol and study records with the Investigator(s) and their staff. During the study, the study monitor will visit the site regularly to check the completeness of subject records, the accuracy of entries into the study database, the adherence to the protocol and to GCP, the progress of enrollment, to ensure that consent is being sought and obtained in compliance with applicable regulations, and that the investigational product is being stored, dispensed and accounted for according to specifications. The Investigator and key trial personnel must be available to assist the monitor during these visits.

The Investigator must give the monitor access to relevant hospital or clinical records to confirm their consistency with the study database entries. No information in these records about the identity of the subjects will leave the study center. Monitoring standards require full verification for the presence of informed consent, adherence to the inclusion/exclusion criteria, documentation of SAEs and the recording of primary efficacy and safety variables. Additional checks of the consistency of the study records with the study database will be performed according to the study-specific monitoring plan.

The Investigator or designee must promptly enter the data into the study database after the subject's visit. The monitor is responsible for reviewing them and clarifying and resolving any data queries. A copy of the study records will be retained by the Investigator who must ensure that it is stored in a secure place with other study documents, such as the protocol, the Investigator's Brochure and any protocol amendments.

The Investigator must provide PPD and the responsible IRB with a study summary shortly after study completion.

## 10.1 QUALITY ASSURANCE AUDITS AND QUALITY CONTROL

In addition to the routine monitoring procedures, audits of clinical research activities in accordance with SOPs may be performed to evaluate compliance with the principles of GCP. A regulatory authority may also wish to conduct an inspection (during the study or even after its completion). If a regulatory authority requests an inspection, the Investigator must inform PPD immediately that this request has been made.

Study conduct may be assessed during the course of the study by a Quality Assurance representative(s) to ensure that the study is conducted in compliance with the protocol and GCP. He/she will be permitted to inspect the study documents (study protocol, study records, investigational product, original, study-relevant medical records). All subject data will be treated confidentially.

### 11. ETHICS AND RESPONSIBILITY

This study must be conducted in compliance with the protocol, the ICH Guidance for Industry E6 Good Clinical Practice: Consolidated Guidance and the applicable regulatory requirements. The Investigator must submit all essential regulatory documentation, as required by local and national regulations (including approval of the protocol and informed consent/assent form by an IRB) to PPD before investigational product will be shipped to the study site. The Investigator will review the final study results to confirm that to the best of his knowledge, it accurately describes the conduct and results of the study.

### 12. CONFIDENTIALITY

All information generated in this study must be considered highly confidential and must not be disclosed to any persons not directly concerned with the study without written prior permission from Novan. Authorized regulatory officials, PPD and Novan personnel (or their representatives) will be allowed full access to inspect and copy the records. All study investigational products, subject bodily fluids, and/or other materials collected shall be used solely in accordance with this protocol, unless otherwise agreed to in writing by Novan.

Subjects will only be identified by unique subject numbers in the study database.

### 13. AMENDMENT POLICY

Only Novan may modify the protocol. Amendments may be approved by all applicable national and local committees including, but not limited to, the government regulatory authorities and/or regional IRB before implementation. The only exception is when an Investigator considers that a subject may be harmed and immediate action is necessary. Under these circumstances, approval of the chairman of the IRB, or an authorized designee must be sought immediately. The Investigator should inform PPD and the full IRB no later than five working days after the

emergency occurs. Protocol-specified safety reporting requirements must be adhered to independent of any other variables. All amendments that have an impact on subject risk, the study objectives or that require revision of the informed consent document must be approved by the IRB before implementation. Administrative changes to the protocol and/or changes that do not impact subject safety, risk or comfort may be implemented prior to IRB approval if local institutional policy permits. A copy of the written approval of the IRB, which becomes part of the essential study documents file, must be given to the study monitor. Examples of amendments requiring such approval are:

- A significant change in the study design
- An increase in the number of invasive procedures to which subjects are exposed
- An addition or deletion of a test procedure

The Principal Investigator at each study site must sign the Investigator's Agreement page of the amended protocol.

### 14. USE OF INFORMATION AND PUBLICATION

It is understood by the Investigator that the information generated in this study will be used by Novan in connection with the development of the product and therefore may be disclosed to government agencies in various countries. To allow for the use of information derived from the study, it is understood that the Investigator is obliged to provide PPD and Novan with complete test results, all study data and access to all study records.

Investigators may not report the results of this clinical study in any publication, poster or other public forum without express authorization from Novan.

## 16. APPENDICES

## 16.1APPENDIX 1: LIST OF RESTRICTED MEDICATIONS AND SUPPLEMENTS:

- Anti-wart medications including but not limited to imiquimod, condylox, sinecatechins
- Benzocaine & Cetacaine sprays
- Corticosteroids (oral)
- Dapsone
- EMLA Creams
- Chloroquine
- Flutamide
- L-arginine
- L-citrulline
- Lidocaine
- Nitric oxide supplements
- Nitrates
- Nitric oxide
- Nitroglycerin
- Nitroprusside
- Nitrous oxide

## LIST OF ABBREVIATIONS

Abbreviation	Definition
AE	adverse event
CI	confidence interval
DSMB	data safety monitoring board
eCRF	electronic case record form
ET	early termination
EGW	external genital warts
FDA	Food and Drug Administration
HPV	human papilloma virus
IB	Investigator's Brochure
ICF	informed consent form
ICH	International Conference on Harmonisation
ITT	intent-to-treat
IVRS/IWRS	interactive voice response system/interactive web response system
LOCF	last observation carry forward
MedDRA	Medical Dictionary for Regulatory Activities
NOVAN	Novan, Inc.
PAW	perianal warts
PP	per-protocol
PT	preferred term
SAE	serious adverse event
SAS	statistical analysis software
SOC	system organ class
TEAE	treatment-emergent adverse events
TIW	three times a week
UPT	urine pregnancy test
WHODD	World Health Organization Drug Dictionary
WOCBP	women of child-bearing potential

## 1. Introduction

External genital warts (EGW) and perianal warts (PAW) are a common sexually transmitted disease due to infection with human papillomavirus (HPV). Current EGW/PAW treatments include local destructive procedures and topical treatments. These treatments are associated with local application site adverse reactions and wart recurrence rates of 10-30%.

Nitric oxide is a free radical gas naturally produced by the human body which has anti-virucidal and anti-inflammatory activity. Novan, Inc. has developed a topical gel containing NVN1000, a drug which releases nitric oxide to the skin after application. In an animal model of skin papillomas, topical NVN1000 gel prevented wart growth in a dose responsive fashion.

NVN1000 is also in development for the treatment of acne vulgaris. To date, approximately 400 subjects have been treated with NVN1000 Gel, and 200 subjects have been treated with the Vehicle Gel. In the completed studies for acne vulgaris, NVN1000 Gel has been generally safe and well tolerated.

Novan is conducting this Phase 2, variable dose, randomized, double-blind study to assess tolerability, safety and efficacy of topical NVN1000 in subjects with EGW/PAW.

#### 2. Objectives

The objectives of this study are to assess tolerability, safety and efficacy of topical NVN1000 Gel and Vehicle Gel for up to 12 weeks in subjects with EGW/PAW.

#### 3. Investigational Plan

#### 3.1. Overall Study Design and Plan

Subjects will dose for up to 12 weeks (84 days) with NVN1000 Gel or Vehicle Gel coadministered with an equal volume of a carboxymethyl cellulose hydrogel. Subjects will be randomized 3:1 to active:vehicle in 4 dose cohorts initiated at NVN1000 8% Gel. The safety/tolerability of each cohort will be assessed by an independent data safety monitoring board (DSMB) after the first 12 subjects of each cohort complete 2 weeks of dosing.

Figure 3–1 depicts the overall study design for this 12 week, variable dose, randomized, double blind study in subjects with EGW/PAW dosed with NVN1000 Gel or Vehicle Gel. Subjects receiving current treatment for EGW/PAW may enter a wash out period after screening of up to 35 days prior to randomization.

Subjects who are found to be cleared of all warts at a visit will discontinue treatment at that time. If warts recur at a subsequent visit prior to end of treatment, subjects will be dispensed a new kit of the same treatment they previously received.

		Vehicle Gel	to match cohort	dosing	
			el 8% twice dai	ly (Cohort 1)	
	Randomization: 3:1	- NVN1000 C	el 8% once dail	y (Cohort 2)	
	active.venicle	- NVN1000 C	el 16% once dai	ily (Cohort 3)	
		- NVN1000 C	el 24% once dai	ily (Cohort 4)	
Visits		T T' '. 1			
Screening	Baseline	Visit I	Visit 2	Visit 3	Visit 4/ET
Day -35 to Day -1	Day 0	Day 14	Day 28	Day 56	Day 84
	Study Week	2	4	8	12

Figure 3–1: Study Diagram

## 3.2. Study Endpoints

### **3.2.1.** Primary Efficacy Endpoint

• Proportion of subjects with complete clearance of baseline EGW/PAW at or before Week 12

#### 3.2.2. Secondary Efficacy Endpoints

The secondary endpoints will include:

• Proportion of subjects with complete clearance of total EGW/PAW at or before Week 12

- Proportion of subjects with a complete or partial clearance of baseline EGW/PAW at or before Week 12. A partial clearance is defined as a reduction in the number of baseline warts.
- Proportion of subjects with complete clearance of baseline EGW/PAW at Weeks 2, 4, 8, and 12
- Proportion of subjects with complete clearance of total EGW/PAW at Weeks 2, 4, 8, and 12
- Proportion of subjects with a complete or partial clearance of baseline EGW/PAW at Weeks 2, 4, 8, and 12
- Count of baseline warts and count of total warts at Weeks 2, 4, 8, and 12
- Percent and raw reduction in baseline EGW/PAW wart counts at Weeks 2, 4, 8, and 12
- Time to complete clearance of baseline warts
- Recurrence of baseline warts cleared prior to Week 12

### **3.2.3.** Tolerability Endpoints

The tolerability assessments include the investigator's assessment of erythema, edema, erosions/ulcers, and the subject's report of burning/stinging based on the preceding 24 hours on a 4 point (0-3) scale.

#### 3.2.4. Safety Endpoints

Safety endpoints will include adverse events (AEs), laboratory tests including change from baseline in percent methemoglobin, chemistry, hematology, and prothrombin time (PT)/partial thromboplastin time (PTT) values, change from baseline on physical examination including vital sign measurements. Any clinically significant changes noted during the physical examination including the vital sign measurements, or safety laboratory assessments will be recorded as AEs.

#### 4. General Statistical Considerations

All statistical processing will be performed using SAS® version 9.2 or higher unless otherwise stated. Statistical significance will be based on two-tailed tests of the null hypothesis resulting in p-values of  $\leq 0.05$  unless stated otherwise. Inferential testing will compare each active treatment group to the vehicle treatment group. Comparisons will not be performed between active treatments. All p-values will be reported without concern for controlling for multiplicity. Efficacy analyses will be performed for the intent-to-treat (ITT) and per-protocol (PP) populations. Safety analyses will be performed using the safety population as defined in section 4.3.2

Continuous data will be summarized with sample size (N), mean, median, standard

deviation, minimum and maximum. Categorical data will be summarized with number of subjects N, frequency counts, and percentages.

For analysis, baseline warts are defined as warts that are present at the baseline visit. Total warts include all warts present, even if they were not present at the baseline visit. Complete clearance is defined as zero warts present. Partial clearance is defined as a reduction in number of warts from baseline.

The last evaluation for each endpoint prior to the first dose of study drug will be used as baseline for all analyses.

For safety analyses including tolerability, summaries will be performed by treatment arm as well as "Pooled Active", which is a total of all NVN1000 treatment arms.

For disposition, demographics, efficacy, compliance and tolerability analyses, Vehicle Gel subjects will be summarized separately by dosing frequency (QD and BID). For other safety analyses, vehicle subjects will be combined. Subjects will be listed by actual treatment, with vehicle subjects listed separately by dosing frequency.

For subjects who are taken off treatment due to complete clearance of warts and then later restart treatment due to recurrent warts, the date of last dose for analysis purposes will be the date of last dose for the second treatment interval.

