# **Exclusion Criteria:**

- History of neoplasia including cervical intraepithelial neoplasia on 2/3, invasive cervical carcinoma, or other HPV associated malignancies within 5 years or current neoplasia (with the exception of non-melanoma skin cancer on non-genitals);
- Any recent (< 6 months) history of other genital infections, or other genital diseases including Bowens disease, Lichen Sclerosis et Atrophicus, Bowenoid papulosis, erythroplasia of Querat, verrucous carcinoma, lichen planus, and psoriasis that requires use of interfering topical or systemic therapy or makes evaluations and wart counting inconclusive;
- Have active HSV infection of the genitals as defined by initial outbreak within the 2 weeks prior to screening or during the screening period or frequent recurrences (more than 4 events within one year prior to screening) if not receiving HSV suppressive therapy;
- Have received treatment for EGW/PAW during the 28 days prior to

	
 
baseline including podophyllotoxin, imiquimod, sinecatechins, or surgical procedures (cryotherapy, laser surgery, cold steel, electorfulgeration);
 
Have a confirmed methemoglobin level of > 3.0% at Screening or Baseline per handheld pulse co-oximeter device;
 
Have hemoglobin at Screening < 10 g/dL.
 
					
Sample Size	Approximately 120 subjects will be randomized into the study in a 3:1 ratio of active:vehicle in 4 different cohorts.					
Safety/Tolerability Assessments						
Endpoints	Tolerability Endpoint: Tolerability of NVN1000 Gel and Vehicle Gel will be collected using a 4 point tolerability scale to assess erythema, erosions/ulcers, edema and stinging/burning.  Safety Endpoints: Safety endpoints will include adverse events, changes in physical examination including vital signs and changes in laboratory examination including methemoglobin. Any clinically significant changes noted during the physical exam as well as from the vital sign measurements or laboratory examinations will be recorded as adverse events and included in the comparison.					
	Efficacy Endpoints: For all efficacy analyses, unless otherwise specified, efficacy will be based on warts which are present at baseline.  Selected summaries will be presented for total warts. Total wart summaries will be based on any wart(s) observed at the given visit, including warts that were not present at baseline.					

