### 3.2 STRUCTURE

This is a variable dose, double-blind, multi-center, randomized, vehicle-controlled, 4-arm study. Dosing initiated at NVN1000 8% Gel twice daily. Amendement 1 modified Cohort 2 dosing to NVN1000 8% once daily based on local intolerability observed in two subjects randomized in Cohort 1. Cohort 3 will be dosed with NVN1000 16% once daily and Cohort 4 will be dosed with NVN1000 24% once daily. An independent Data Safety Monitoring Board (DSMB) will review

tolerability and safety data approximately 2 weeks after randomization of the 12th subject in each cohort to determine whether dosing shall change. Subjects will continue to enroll and accrue in the open dosing cohort pending the DSMB review. Upon completion of the DSMB review, the recommendations of the DSMB regarding dosing will be implemented.

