### 4.3 TOLERABILITY ASSESSMENTS

The Investigator will evaluate the subject's genital/perianal area prior to the first application of investigational product in addition to evaluating at each study visit. The tolerability assessment for visits other than Baseline should be performed at least 30 minutes after study drug application and prior to wart counts. Tolerability evaluations will include erythema, edema, erosions/ulceration and burning/stinging. Burning/stinging will be based on the subject's report

of local symptoms for the previous 24 hours. The highest severity of each parameter will be recorded. Tolerability endpoints will not be reported as an AE unless they reach severe and/or result in subject's discontinuation from the study. Tolerability assessments will be performed according to the following scales:

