#### 8.1. Primary Efficacy Endpoint

## 8.1.1. Proportion of Subjects with Complete Clearance of Baseline EGW/PAW at or Before Week 12

The primary efficacy endpoint is the proportion of subjects with complete clearance of baseline EGW/PAW at or before Week 12.

The number and proportion of subjects with complete clearance of baseline warts will be summarized by treatment group and each active dose group will be compared to vehicle using pairwise Pearson's chi-square tests. The Mantel-Haenszel odds ratios and corresponding 95% confidence interval (CI) will be presented. The Vehicle Gel arm will be separated into once-daily (QD) and twice-daily (BID) groups and compared pairwise to the corresponding active treatments. The three once-daily active treatment groups (8%, 16%, and 24%) will be compared to the Vehicle Gel QD group and the NVN1000 8% BID group will be compared to the Vehicle Gel BID group. The pairwise comparisons will be computed without concern for controlling for multiplicity. The primary analysis will be performed for the ITT population.

Percentages will be calculated based on the number of subjects in the ITT analysis population. Subjects who have clearance of baseline warts at or before the Week 12 visit will be counted as cleared for the analysis. Subjects who do not have a documented clearance by the end of study, including subjects with missing data at the Week 12 or other assessments, will be considered not cleared for the analysis.

The primary analysis will be repeated for the PP population. Subgroup analysis for gender and wart location (EGW/PAW) will also be performed for the ITT population. The subgroup summaries will be descriptive only with no statistical hypothesis testing performed.

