#### **Burning/Stinging**

Score	Description
0-None	No burning/stinging
1-Mild	Slight warm, burning/stinging sensation; not very bothersome
2-Moderate	Definite warm, burning/stinging sensation that is somewhat bothersome
3-Severe	Hot, tingling/sensation that has caused definite discomfort and may
	have disturbed sleep

Tolerability assessments (erythema, edema, erosions/ulcerations, burning/stinging) will be summarized using frequency distributions at baseline, Weeks 2, 4, 8, and 12/ early termination (ET), as well as the worst post-baseline assessment. The worst post-baseline assessment will be determined individually for each tolerability parameter. (e.g., the worst assessment for erythema may occur at a different visit than the worst assessment for edema.) The number and proportion of subjects with a severe assessment or a two step severity increase from baseline will be summarized by treatment group at Weeks 2, 4, 8, and 12/ET for each assessment and for any assessment. Vehicle Gel subjects will be separated into QD and BID groups. Additionally, the number and percentage of subjects who have 2 or more severe assessments at the same visit for any visit will be presented. A shift table will also be presented by tolerability parameter and treatment group, and all tolerability scores will be listed.

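### TEAE tables combine once-daily and twice-daily vehicle, so the 8% twice-daily arm has no frequency-matched vehicle column there (minor; cheap to improve)

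*SAP*

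**What the plan says.** SAP section 4 (General Statistical Considerations) sets two rules for vehicle. For disposition, demographics, efficacy, compliance and tolerability, "Vehicle Gel subjects will be summarized separately by dosing frequency (QD and BID"). It then adds "For other safety analyses, vehicle subjects will be combined". Adverse events fall under the second rule, and SAP sections 9.1 to 9.4 restore no split. The same section keeps the active arms separate in safety tables and adds a Pooled Active column. No reason is given for treating adverse events differently.

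Elsewhere the match by frequency is kept:

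- Efficacy (SAP 8.1.1): "The Vehicle Gel arm will be separated into once-daily (QD) and twice-daily (BID) groups and compared pairwise to the corresponding active treatments".
- Tolerability (SAP 8.3): "Vehicle Gel subjects will be separated into QD and BID groups".
- Disposition, including reasons for discontinuation (SAP 5.2), and exposure and compliance (SAP 7.2.1): vehicle is split.
- Listings (SAP 4): "Subjects will be listed by actual treatment, with vehicle subjects listed separately by dosing frequency".

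Only Cohort 1 is dosed twice daily; Cohorts 2 to 4 are once daily (Protocol 3.2 and 3.4). Vehicle follows the dosing of its cohort (SAP Figure 3-1).

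**The concern.** Randomization is 3:1 within each cohort (Protocol 8.3), so the BID vehicle subjects are the concurrent, frequency-matched control for 8% BID. The TEAE tables merge them into a vehicle group that is probably mostly QD.

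The documents give some reason to think that frequency could matter. Protocol 1.5 says local reactions may come from the active agent or the vehicle. Cohort 2 was moved from twice to once daily "based on local intolerability observed in two subjects randomized in Cohort 1", and Protocol 1.5 says that it was not known at the time which treatment those two subjects had received. Whether local reactions follow drug, vehicle or frequency is therefore an open question in this trial, and a TEAE table with one vehicle column cannot help to answer it for a single arm.

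If BID vehicle produces more adverse events than QD vehicle, the combined column is too low a reference for 8% BID and too high a reference for the three QD arms. Interim Table 14.3.1-2 has the same layout, and SAP section 10 says the interim is meant to help plan future trials.

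**Working it through.** **Inputs.** The synopsis states: "Approximately 120 subjects will be randomized into the study in a 3:1 ratio of active:vehicle in 4 different cohorts". That gives 120/4 = 30 vehicle subjects. Cohort sizes are not fixed: Protocol 7.8 and SAP 4.1 leave them to the DSMB and enrollment. Vehicle adverse-event rates are not given, so the rates below are assumptions for illustration. The plan states no vehicle mix or adverse-event rate, so there is no figure of its own to reproduce.

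**QD share of combined vehicle.** With n1 subjects in Cohort 1, BID vehicle = n1/4 and the QD share is s = 1 − (n1/4)/30.

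**Bias.** With vehicle rates pQ (QD) and pB (BID), combined vehicle = s·pQ + (1 − s)·pB. The 8% BID excess is overstated by pB − combined = s(pB − pQ). Each QD excess is understated by combined − pQ = (1 − s)(pB − pQ). Both are zero when pB = pQ.

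With pQ = 10% and pB = 20% (assumed):

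| Cohort 1 size (of 120) | BID / QD vehicle | QD share | Combined vehicle | BID excess overstated | QD excess understated |
|---|---|---|---|---|---|
| 12 | 3 / 27 | 90% | 11% | 9 points | 1 point |
| 30 (equal cohorts) | 7.5 / 22.5 | 75% | 12.5% | 7.5 points | 2.5 points |
| 48 | 12 / 18 | 60% | 14% | 6 points | 4 points |
| Interim, Cohorts 1 and 2 equal | equal | 50% | 15% | 5 points | 5 points |

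The size depends on the assumed rates. At a 75% share, rates of 5% and 10% give 3.75 and 1.25 points; rates of 10% and 30% give 15 and 5 points.

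**Pooled contrast.** The BID share of Pooled Active is (3n1/4)/(3·120/4) = n1/120. The BID share of combined vehicle is (n1/4)/(120/4) = n1/120. They agree for any cohort sizes, so only arm-level readings are affected.

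**Precision of a split column.** With equal cohorts, BID vehicle is 7 or 8 subjects. Zero events leaves a one-sided 95% upper bound of 1 − 0.05^(1/7) = 35% or 1 − 0.05^(1/8) = 31%, against 9.5% for 30. At a common rate of 20%, the standard error of the 8% BID difference is √[0.16(1/22.5 + 1/7.5)] = 0.169 against BID vehicle, and √[0.16(1/22.5 + 1/30)] = 0.112 against combined vehicle.

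**The case against.** A reader might infer that the most serious local reactions lose their matched control, because Protocol 4.3 says "Tolerability endpoints will not be reported as an AE unless they reach severe and/or result in" discontinuation from the study. The documents do not support that. SAP 8.3 tabulates, with vehicle split, severe scores or two-step increases at each visit and the worst post-baseline score, and it also counts subjects with two or more severe scores at the same visit. SAP 5.2 summarizes reasons for discontinuation with vehicle split, and Adverse Event is one of the reasons in Protocol 4.1.7. Adverse events leading to discontinuation are planned as a listing (SAP 9.1.5), and listings separate vehicle by frequency. The interim package includes the disposition and tolerability tables. The severe erythema, burning or erosions described for the two Cohort 1 subjects are all scored signs.

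Three further points stand. SAP 9.1 plans counts and percentages with no tests, so 8% BID is not formally judged against combined vehicle. No document says that BID vehicle is worse than QD vehicle. One event in 7 or 8 subjects moves the rate by 13 to 14 points (1/8 = 12.5%, 1/7 = 14.3%), more than the 7.5-point bias in the illustration; combining vehicle in sparse tables is a defensible choice, though the SAP does not give that reason.

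These points narrow the gap without closing it. Contact dermatitis, peeling and scaling are named in Protocol 1.5 but are not scored signs, so their summary rates appear only in TEAE tables. A reaction that begins and resolves between visits may be missed by the scores: burning/stinging covers only the previous 24 hours. Listings allow counting by hand but give no rates.

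**Conclusion.** The point holds as a minor gap in presentation. The TEAE tables offer no frequency-matched vehicle rate for the only BID active arm, although the SAP keeps that match in its other main comparisons.

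With assumed vehicle rates of 10% QD and 20% BID, the 8% BID excess may be overstated by 7.5 points with equal cohorts (6 to 9 points for QD shares of 60% to 90%). Each QD excess may be understated by 2.5 points (1 to 4 points). This rests on a frequency effect that the documents make plausible but do not show.

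It would be wrong to state as fact that 8% BID will look worse than it is, or that combined vehicle is 75% QD. The first needs the unproven rate difference. The second needs equal cohorts, which the documents do not promise.

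**What to change.** In SAP sections 4 and 9.1, present the TEAE tables (overall, SOC and preferred term, severity, relatedness) with three vehicle columns: Vehicle QD, Vehicle BID and combined Vehicle. Do the same in interim Table 14.3.1-2. Adverse events leading to discontinuation need no change, since their listing is already split by frequency.

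The cost is two extra columns in existing tables. The BID vehicle column will be imprecise, which is why the combined column should stay beside it.
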